#### **4.3.1.2 Dose Escalation for R/R AML**

In the Dose Escalation, the R/R AML Cohort will be initiated after the DL of 16 mg/kg in the RRMM Cohort has been cleared by the Safety Committee. Preliminary safety, PK, and pharmacodynamic data of GEN3014 at DLs up to 16 mg/kg in RRMM subjects will be reviewed, supported by PK/pharmacodynamic modeling and exposure-safety analyses. CCI

[REDACTED]

CCI

[REDACTED]

[REDACTED]

[REDACTED]

CCI

[REDACTED]

CCI

[REDACTED]

#### **4.3.2 Expansion Part A (GEN3014 Single Cohorts)**

The GEN3014 dose for Expansion Part A (GEN3014 Single Cohorts) subjects with anti-CD38 mAb-naïve RRMM, anti-CD38 mAb-refractory RRMM, and R/R DLBCL will be the RP2D which is based on assessment of all available data from the Dose Escalation part of this trial. The rationale to use the same RP2D for R/R DLBCL is based on the observation that the PK and safety profiles of daratumumab in B-NHL subjects including DLBCL are similar to MM subjects (Salles et al., 2019). Based on assessment of all available data from the Dose Escalation part of this trial, 16 mg/kg was selected as the RP2D.

Subjects with R/R AML will be treated with GEN3014 at the RP2D identified for R/R AML from the Dose Escalation.

The GEN3014 administration schedule is based upon the primary results of the daratumumab GEN501 and SIRIUS studies, and similar mechanism of action between GEN3014 and daratumumab (Usmani et al., 2020).

### **4.3.3 Expansion Part B (Randomized H2H)**

The GEN3014 dose for Expansion Part B (Randomized H2H) for subjects with anti-CD38 mAb-naïve RRMM will be the RP2D from the Dose Escalation part of this study, which was determined to be 16 mg/kg. The GEN3014 administration schedule is based upon the primary results of the daratumumab GEN501 and SIRIUS studies (Usmani et al., 2020). The first administration is split 50%/50% between 2 consecutive days (Cycle 1 Days 1 and 2) to accommodate long infusion durations and to control anticipated IRRs. The daratumumab SC dose will be at the approved dose of 1800 mg. The approved administration schedule for daratumumab SC monotherapy will be used. The schedule is the same as for GEN3014 except for the Cycle 1 Day 1/Day 2 split of the first administration, which is not warranted for SC dosing.

### **4.4 End of Trial Definition – Dose Escalation, Expansion Part A (GEN3014 Single Cohorts), and Expansion Part B (Randomized H2H)**

The end of trial is defined as the last date of data collection for the last subject in the trial globally. In this trial, the maximum trial duration is 5 years after the last subject's first treatment in the trial.

#### **4.4.1 Estimated Trial Duration for an Individual Subject**

##### ***4.4.1.1 Dose Escalation***

The estimated trial duration for an individual subject with RRMM is 22 months, consisting of up to 21-day screening period, an estimated 4-month treatment period (the duration of treatment may vary for each subject), and an estimated 17-month post-treatment follow-up period (the duration of follow-up may vary for each subject).

The estimated trial duration for an individual subject with AML is 9 months, consisting of up to 21-day screening period, an estimated 3-month treatment period (the duration of treatment may vary for each subject), and an estimated 5-month post-treatment follow-up period (the duration of follow-up may vary for each subject).

##### ***4.4.1.2 Expansion Part A (GEN3014 Single Cohorts)***

The estimated trial duration for an individual subject with RRMM is 22 months, consisting of up to 21-day screening period, an estimated 4-month treatment period (the duration of treatment may vary for each subject), and an estimated 17-month post-treatment follow-up period (the duration of follow-up may vary for each subject).

The estimated trial duration for an individual subject with DLBCL is 15 months, consisting of up to 21-day screening period, an estimated 4-month treatment period (the duration of treatment may vary for each subject), and an estimated 10-month post-treatment follow-up period (the duration of follow-up may vary for each subject).

##### ***4.4.1.3 Expansion Part B (Randomized H2H)***

The estimated trial duration for an individual subject is 22 months, consisting of up to 21-day screening period, an estimated 4-month treatment period (the duration of treatment may vary for each subject), and an estimated 17-month post-treatment follow-up period (the duration of follow-up may vary for each subject).

## 5 TRIAL POPULATION

The inclusion and exclusion criteria for enrolling subjects are described in Sections 5.1 and 5.2, respectively. Screening for eligible subjects will be performed during a 21-day period prior to the first dose of GEN3014 (Dose Escalation of GEN3014; Expansion Part A of GEN3014 in anti-CD38 mAb-naïve RRMM Cohort, anti-CD38 mAb-refractory RRMM Cohort, R/R DLBCL Cohort, and R/R AML Cohort) or Expansion Part B (Randomized H2H). For the Expansion Part B, the eligibility information will be submitted to the sponsor's medical monitor for review prior to randomization. If the sponsor agrees that the eligibility criteria have been met, then the investigator will receive confirmation that the subject may be randomized into the study. If the sponsor considers that the eligibility criteria have not been met, then the sponsor will contact the investigator to discuss the subject. If there is a question about the inclusion or exclusion criteria, the investigator must consult with the sponsor's medical monitor and resolve any issues before enrolling a subject in the study.

### 5.1 Inclusion Criteria

#### 5.1.1 Inclusion Criteria – Dose Escalation

Each potential subject must fulfill all of the following criteria to be eligible for inclusion in the Dose Escalation part of the trial:

1. Must be at least 18 years of age.
2. Must sign an informed consent form (ICF) prior to any Screening procedures. Where required by local or country specific regulations, each subject must sign a separate ICF if he or she agrees to provide samples for genomic biomarker analysis (deoxyribonucleic acid [DNA] and ribonucleic acid [RNA]).
3. Must have fresh bone marrow samples collected at Screening.
4. Eastern Cooperative Oncology Group (ECOG) performance status (PS) score 0, 1, or 2.
5. Criterion modified per Amendment 2.

5.1 Criterion modified per Amendment 3\_US-1.

5.2 Criterion modified per Amendment 4.

5.3 Has acceptable laboratory test results during the Screening period, as follows:

Parameter		Result
a.	Creatinine clearance (CrCl) or serum creatinine	CrCl $\geq 50$ mL/min estimated by Cockcroft-Gault (see Section 10.5) or serum creatinine $\leq 1.5 \times$ upper limit of normal (ULN)
aUS	CrCl	See Section 10.15.2 for requirements per local health authorities.
b.	Serum alanine aminotransferase (ALT)	$\leq 2.5 \times$ ULN
c.	Serum aspartate aminotransferase (AST)	$\leq 2.5 \times$ ULN
d.	Total bilirubin	$\leq 2 \times$ ULN  Note: A subject with Gilbert's syndrome may be included if total bilirubin is <math>\leq 3 \times</math> ULN and direct bilirubin is <math>\leq 1.5 \times</math> ULN

e.	Hemoglobin	$\geq 8$ g/dL ( $\geq 80$ g/L or $\geq 5$ mmol/L) for RRMM Note: Red blood cell transfusion may be administered during Screening to meet this requirement
f.	Absolute neutrophil count	$>1.0 \times 10^9$ /L ( $>1,000/\mu\text{L}$ ) for RRMM Note: G-CSF may be administered during Screening to meet this requirement
g.	Platelet count	$>50 \times 10^9$ /L ( $>50,000/\mu\text{L}$ ) for RRMM Note: Platelet transfusion may be administered during Screening to meet this requirement
h.	Coagulation Status: Prothrombin time (PT), International normalized ratio (INR), activated partial thromboplastin time (aPTT)	PT/INR/aPTT $\leq 1.5 \times \text{ULN}$

6. A woman of reproductive potential must agree to use adequate contraception during the trial and for 12 months after the last GEN3014 administration. Adequate contraception is defined as highly effective methods of contraception (refer to Section 10.4 Appendix 4: Contraceptive Guidance and Collection of Pregnancy Information). In countries where 2 highly effective methods of contraception are required, both methods will be required for inclusion.
7. A woman of childbearing potential must have a negative serum beta-human chorionic gonadotropin ( $\beta$ -hCG) at Screening.
8. A woman must agree not to donate eggs (ova, oocytes) for the purposes of assisted reproduction during the trial and for 12 months after receiving the last dose of GEN3014.
9. A man who is sexually active with a woman of childbearing potential and has not had a vasectomy must agree to use a barrier method of birth control, eg, either condom with spermicidal foam/gel/film/cream/suppository or partner with occlusive cap (diaphragm or cervical/vault caps) with spermicidal foam/gel/film/cream/suppository, and all men must also not donate sperm during the trial and for 12 months after receiving the last dose of GEN3014.

#### **Specific Inclusion Criteria for RRMM:**

##### 10. Criterion modified per Amendment 1.

10.1 Must have documented multiple myeloma as defined by the criteria below and have evidence of disease progression on the most recent prior treatment regimen based on IMWG criteria:

- Prior documentation of monoclonal plasma cells in the bone marrow  $\geq 10\%$  or presence of a biopsy-proven plasmacytoma.

**and**

- Measurable disease at baseline as defined by any of the following:
  - IgG, IgA, IgD, or IgM myeloma: Serum M-protein level  $\geq 0.5$  g/dL ( $\geq 5$  g/L) or urine M-protein level  $\geq 200$  mg/24 hours;

**or**

- Light chain myeloma: Serum Ig free light chain (FLC)  $\geq 10$  mg/dL and abnormal serum Ig kappa lambda FLC ratio.

Note: Subjects with RRMM must have exhausted standard therapies, at the investigator's discretion.

11. Criterion modified per Amendment 2.

11.1 Criterion modified per Amendment 1.

11.2 Criterion modified per Amendment 1\_SE-1.

11.3 Criterion modified per Protocol Amendment\_FR-1.

11.4 For anti-CD38 mAb-naïve RRMM subjects: Subject received at least 3 prior lines of therapy including a PI and an IMiD in any order or is double refractory to a PI and an IMiD; or subject received  $\geq 2$  prior lines of therapy if 1 of those lines included a combination of PI and IMiD. Note: Subjects should not have received any anti-CD38 antibody. Anti-CD38 mAb-naïve RRMM subjects may be recruited from Sweden, France, Spain, Netherlands, and Australia, and from countries where anti-CD38 therapies are not available.

12. Criterion modified per Amendment 2.

12.1 Criterion modified per Protocol Amendment\_FR-1.

12.2 For anti-CD38 mAb-treated RRMM subjects: Subject has received at least 2 prior lines of therapy and must have discontinued daratumumab or isatuximab for at least 4 weeks prior to the first dose of GEN3014. Note: Subjects should not have received any other anti-CD38 antibody except daratumumab or isatuximab.

13. Criterion modified per Amendment 2.

13.1 Criterion modified per Amendment 3.

13.2 Potassium level  $\geq 3.0$  mEq/L ( $\geq 3.0$  mmol/L); and corrected serum calcium  $\leq 14.0$  mg/dL ( $\leq 3.5$  mmol/L) or free ionized calcium  $\leq 6.5$  mg/dL ( $\leq 1.6$  mmol/L) (see formula for corrected serum calcium in Section 10.7).

**Specific Inclusion Criteria for R/R AML:**

14. Criterion modified per Amendment 1.

14.1 Criterion modified per Amendment 4.

14.2 Relapsed or refractory **CCl** AML, both de novo or secondary; must have failed all conventional therapy. Acute promyelocytic leukemia (APL) is excluded from this trial. Note: Relapse is defined by BM blasts  $\geq 5\%$  in patients who have been in complete remission (CR) previously, or reappearance of blasts in the blood, or development of extramedullary AML. Refractory is defined as not being able to achieve a CR after the initial therapy. **CCl**

15. Subject with relapsed AML who received at least 2 prior therapies for AML with the exception of hydroxyurea.

16. Subject with refractory AML who received at least 1 prior line of therapy for AML with the exception of hydroxyurea.

17. Subject's life expectancy at Screening is judged to be at least 3 months.

### 5.1.2 Inclusion Criteria – Expansion Part A (GEN3014 Single Cohorts)

Each potential subject must fulfill all of the following criteria to be eligible for inclusion in the Expansion Part A of the trial:

1. Must be at least 18 years of age.
2. Must sign an ICF prior to any Screening procedures. Where required by local or country specific regulations, each subject must sign a separate ICF if he or she agrees to provide samples for genomic biomarker analysis (DNA and RNA).
3. ECOG PS score 0, 1, or 2 for MM and AML; ECOG PS 0 or 1 for DLBCL.
4. Must have fresh bone marrow samples collected at Screening. This requirement does not apply to R/R DLBCL subjects who are suspected to have bone marrow involvement.
5. Criterion modified per Amendment 2.

5.1 Criterion modified per Amendment 3\_US-1.

5.2 Criterion modified per Amendment 4.

5.3 Has acceptable laboratory test results during the Screening period, as follows:

Parameter		Result
a.	Creatinine clearance (CrCl) or serum creatinine	CrCl $\geq 50$ mL/min estimated by Cockcroft-Gault (see Section 10.5) or serum creatinine $\leq 1.5 \times$ upper limit of normal (ULN)
b.	Serum alanine aminotransferase (ALT)	$\leq 2.5 \times$ ULN
c.	Serum aspartate aminotransferase (AST)	$\leq 2.5 \times$ ULN
d.	Total bilirubin	$\leq 2 \times$ ULN Note: A subject with Gilbert's syndrome may be included if total bilirubin is <math>\leq 3 \times</math> ULN and direct bilirubin is <math>\leq 1.5 \times</math> ULN
e.	Hemoglobin	$\geq 8$ g/dL ( $\geq 80$ g/L or $\geq 5$ mmol/L) for RRMM and R/R DLBCL Note: Red blood cell transfusion may be administered during Screening to meet this requirement
f.	Absolute neutrophil count	$> 1.0 \times 10^9$ /L ( $> 1,000/\mu\text{L}$ ) for RRMM and R/R DLBCL Note: G-CSF may be administered during Screening to meet this requirement
g.	Platelet count	$> 50 \times 10^9$ /L ( $> 50,000/\mu\text{L}$ ) for RRMM and R/R DLBCL Note: Platelet transfusion may be administered during Screening to meet this requirement
h.	Coagulation Status: Prothrombin time (PT), International normalized ratio (INR), activated	PT/INR/aPTT $\leq 1.5 \times$ ULN

	partial thromboplastin time (aPTT)	
--	------------------------------------	--

6. A woman of reproductive potential must agree to use adequate contraception during the trial and for 12 months after the last GEN3014 administration. Adequate contraception is defined as highly effective methods of contraception (refer to Section 10.4 Appendix 4: Contraceptive Guidance and Collection of Pregnancy Information). In countries where 2 highly effective methods of contraception are required, both methods will be required for inclusion.
7. A woman of childbearing potential must have a negative serum  $\beta$ -hCG at Screening.
8. A woman must agree not to donate eggs (ova, oocytes) for the purposes of assisted reproduction during the trial and for 12 months after receiving the last dose of GEN3014.
9. A man who is sexually active with a woman of childbearing potential and has not had a vasectomy must agree to use a barrier method of birth control, eg, either condom with spermicidal foam/gel/film/cream/suppository or partner with occlusive cap (diaphragm or cervical/vault caps) with spermicidal foam/gel/film/cream/suppository, and all men must also not donate sperm during the trial and for 12 months after receiving the last dose of GEN3014.

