DLBCL DISEASE: ASSESSMENTS INCLUDING CENTRAL AND LOCAL LABORATORY ASSESSMENTS															
Immunoglobulins (IgA, IgG, IgM)	8.3.6.2	Also see Table 10-1	X												
Tumor biopsy	8.8.1	A portion of biopsy will be used for biomarker evaluations. Also see Table 1-11	X						X  (C3)				X 		
DLBCL with bone marrow involvement: bone marrow aspirate/biopsy	8.2.3.2	Biopsy obtained as routine standard of care may be used, if taken up to 42 days before C1D1. A portion of bone marrow aspirate/ biopsy will be used for biomarker evaluations. Also see Table 1-11 .	X	Bone marrow biopsy plus aspirate is required for confirmation of an observed radiologic CR; should be done within 30 days of the initial documentation of radiologic CR								X			
FDG-PET-CT/ CT/MRI	8.2.3.1		X	Required at: C2 (W6), C3 (W12), C5 (W18), C6 (W24), then every 24 weeks thereafter (Cycle 12, 18, 24, etc.) until confirmation of disease progression, start of new anti-cancer therapy, withdrawal of consent, or death, whichever comes first								X			

Cycle(s)	Pro- tocol Section	Notes	Screen- ing	Q1W (Weekly)					Q2W		Q4W	UNS	End of Treat- ment	Safety Follow- up 	Survival Status/ contact 
				Cycle 1-2					Cycles 3-6		Cycle 7 onward				
Cycle Day			D -21 to D -1	D1 	D2 (C1 only)	D8	D15	D22	D1	D15	D1		ASAP after last dose	30d after last dose	Q3M
Visit Window							±3d		±3d		±3d		+7d	+7d	±7d
MRI or CT of the brain	8.2.3.1	Perform at Screening only if brain involvement is suspected	X	May be performed during the trial if clinically indicated.											
Response assessment	8.2.3	Response required per efficacy assessment time points		Required at: C2 (W6), C3 (W12), C5 (W18), C6 (W24), then every 24 weeks thereafter (Cycle 12, 18, 24, etc.) until confirmation of disease progression, start of new anti-cancer therapy, withdrawal of consent, or death, whichever comes first								X			
END OF TREATMENT															
New anti-cancer therapy	7.1.1													X	X
Survival Status	7.1.2														X

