Screening or Treatment Cycle (28 days per cycle)	Screening	Cycles 1, 3, 5, 7, and 10	Cycle 13 and onward
Day (window)	Day -21 to Day -1	Day 1 (+2d)	Day 1 (+2d)
Whole blood MRD CCI 	X	X	A whole blood sample will be obtained every 6 months (±1 month) for up to 3 years.
DLBCL with bone marrow involvement: Bone marrow aspirate MRD 	X 	
 
If a subject is in CR, a portion of the aspirate collected to confirm CR will be used to assess MRD; a bone marrow aspirate is then mandatory to confirm MRD negativity.
 
If a subject is MRD positive in the bone marrow but maintains clinical response, an additional bone marrow aspirate will be collected after 3 months, if clinically feasible.
 
	

CR=complete remission; CCI; D/d=day; MRD=minimal residual disease; R/R DLBCL=relapsed or refractory diffuse large B-cell lymphoma.

1. Upon reaching CR on PET-CT scan, an additional blood sample will be collected if not within 2 weeks of another collection to evaluate MRD CCI.

2. CCI.

3. If bone marrow involvement was documented to be absent at Screening, MRD will not be assessed in post-treatment samples.

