### **8.2.3.2 Bone Marrow Assessment**

DLBCL subjects with bone marrow involvement, fresh bone marrow aspirate and biopsy must be obtained at Screening (ie, within 3 weeks prior to the first dose of GEN3014) and at the time of CR or as clinically indicated. A bone marrow biopsy obtained as routine standard of care may be used instead, if taken up to 42 days before first dose of GEN3014. If bone marrow aspirate is obtained, determination of bone marrow involvement may be confirmed by flow cytometry.

- A bone marrow biopsy plus aspirate (performed at local laboratory) is required for confirmation of an observed radiologic CR and should be done preferably within 30 days of the initial documentation of radiologic CR ([Cheson et al., 2014](#)). Bone marrow evaluation must include morphological examination and either flow cytometry or IHC, if warranted, to confirm the presence or absence (CR) of lymphoma. If bone marrow involvement can be confirmed with morphology, flow cytometry/IHC need not be done if this is not part of a trial-site standard practice.

- For subjects having bone marrow involvement documented at Screening, a portion of the aspirate collected to confirm radiologic CR will be used for MRD assessments (see Section 8.8.3 and Table 1-11).
- For subjects having no bone marrow involvement at Screening, no further bone marrow examination for MRD is required.

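### Part A inclusion criterion 4 waives screening marrow for DLBCL subjects suspected of marrow involvement and keeps it for the rest, opposite to Section 8.2.3.2 and Tables 1-7 and 1-11

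*Protocol*

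**What the plan says.** Criterion 4 in Protocol 5.1.2 requires fresh marrow at Screening for Part A and then carves out one group: "This requirement does not apply to R/R DLBCL subjects who are suspected to have bone marrow involvement". The synopsis carries the same sentence.

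The assessment sections define the DLBCL group differently:

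- Section 8.2.3.2: "DLBCL subjects with bone marrow involvement, fresh bone marrow aspirate and biopsy must be obtained at Screening". It allows a substitute: "A bone marrow biopsy obtained as routine standard of care may be used instead, if taken up to 42 days" before the first dose.
- Table 1-7 has a row headed "DLBCL with bone marrow involvement: bone marrow aspirate/biopsy", marked at Screening. The same row holds the on-treatment rule: "Bone marrow biopsy plus aspirate is required for confirmation of an observed radiologic CR".
- Section 8.2.3.2 ties marrow MRD to screening status. One bullet reads "For subjects having bone marrow involvement documented at Screening, a portion of the aspirate collected to confirm radiologic CR will be used" for MRD. The next reads "For subjects having no bone marrow involvement at Screening, no further bone marrow examination for MRD is required".
- Table 1-11 marks a screening aspirate for MRD in DLBCL with marrow involvement. Its footnote 3 says: "If bone marrow involvement was documented to be absent at Screening, MRD will not be assessed in post-treatment samples".

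**The concern.** The eligibility text and the assessment text pick out opposite groups. Sites check eligibility against Section 5 and carry out procedures from Section 8 and the schedules, so both sentences will be used.

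Two things are at stake. First, a subject with no suspected involvement would undergo an invasive procedure only because the entry rule asks for it. Second, a subject with suspected involvement could be entered without the screening marrow on which later rules depend: whether marrow MRD is assessed at all, and whether a marrow is needed to confirm a radiologic CR.

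**Working it through.** No figure in the plan rests on this sentence, so the check is a comparison of texts for the two kinds of DLBCL subject.

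| DLBCL subject | Criterion 4 (5.1.2 and synopsis) | Section 8.2.3.2, Table 1-7, Table 1-11 |
|---|---|---|
| Marrow involvement (criterion 4: suspected) | Fresh screening marrow waived | Screening marrow required |
| No involvement (criterion 4: not suspected) | Fresh screening marrow is a condition of entry | No screening marrow scheduled |

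The rows disagree in both directions.

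**Is the screening marrow of an unsuspected subject used elsewhere?** Table 1-7 lists marrow only in the row for subjects with involvement. Table 1-8 limits the biomarker marrow to MM and AML; the DLBCL biomarker sample is a tumor biopsy. The DLBCL block of Table 10-1 lists no marrow test. The general marrow line in that table is for response assessment, and for DLBCL that leads back to Section 8.2.3.2. No DLBCL schedule calls for the sample.

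**What depends on the screening marrow of a suspected subject?** Marrow MRD on the CR aspirate is for subjects whose involvement was documented at Screening. Table 1-11 footnote 3 switches it off where absence was documented. A suspected subject with no screening result may meet neither condition. The confirmatory marrow at radiologic CR sits in the involvement row of Table 1-7, so unknown status leaves it unclear who needs it.

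**Could this be an artefact?** The sentence is complete in both places and nothing in it is redacted. Criterion 4 carries no amendment note, and the Amendment 5 change list does not mention it.

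**Does it reach the primary endpoint or the design?** SAP 5.3.1 counts PR or CR as response in DLBCL. A CR left unconfirmed by marrow but still at least a PR therefore remains a responder. The two-stage rule (continue with at least 5 of 20; success with at least 13 of 40) was recomputed exactly. The probability of success at response rate p is the sum over x from 5 to 20 of P(X1 = x) × P(X2 ≥ 13 − x), with X1 and X2 each binomial(20, p).

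- p = 0.20 gives 0.0404 (plan: 4.04%).
- p = 0.40 gives 0.8539 (plan: 85.39%).

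Marrow status enters neither figure.

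**The case against.** The strongest reply is that criterion 4 waives an entry condition and does not forbid the procedure. Section 8.2.3.2 still makes the marrow mandatory in subjects with involvement, and Tables 1-7 and 1-11 still mark it. A site that follows the whole protocol collects the baseline. The waiver covers fresh samples, and a routine biopsy up to 42 days old is accepted. This stands: a baseline is lost only where a site relies on the waiver. The substitute is a biopsy, however, while the marrow MRD row of Table 1-11 uses an aspirate.

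The wording also differs: criterion 4 speaks of suspected involvement and Section 8.2.3.2 of involvement. The two groups overlap heavily but are not identical.

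For unsuspected subjects, footnote 3 of Table 1-11 could be read as expecting absence to be established at Screening, perhaps by marrow. That is a possible reading, but the footnote belongs to a row for subjects with involvement, and neither Table 1-7 nor Section 8.2.3.2 schedules a marrow to establish absence.

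A reader might go further and infer that the CR rate or the MRD rate loses its baseline. The documents do not support that:

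- CR is confirmed on an on-treatment marrow. The Lugano criteria in Section 10.14 ask for normal morphology or no FDG-avid marrow disease, and neither compares with baseline. Screening PET-CT, or CT/MRI with FDG-PET, is required in any case.
- SAP 5.6.4 defines MRD negativity on whole blood, which Table 1-11 schedules at Screening. Protocol 9.4.4.1 does not limit the sample type, but the analysis the SAP plans does not need marrow.
- MRD is exploratory in Part A. CR rate is not a listed Part A endpoint, and SAP 5.4.2 says only that it may be shown with the ORR.

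**Conclusion.** The contradiction is real and present in the current text, in both Section 5.1.2 and the synopsis. Followed literally, criterion 4 is wrong in two ways: it makes a marrow with no scheduled DLBCL use a condition of entry for unsuspected subjects, and it waives the sample whose result decides marrow MRD and the need for a confirmatory marrow.

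Its reach is limited. ORR, the Simon design figures and the SAP's whole-blood MRD rate do not change. What is exposed is marrow MRD, the identification of subjects who need marrow confirmation of CR, and an avoidable procedure.

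A reader might want a number of subjects without a baseline. The documents give no prevalence of suspected involvement and no information on how sites apply the waiver, so none can be derived. The rule governs entry for the whole cohort, which is up to 40 subjects, or about 20 if enrollment stops at the futility look.

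**What to change.** Reconcile criterion 4 in Section 5.1.2 and the synopsis with Section 8.2.3.2, Table 1-7 and Table 1-11, so that one and the same DLBCL group is asked for screening marrow in every place. Use a single term, suspected or documented involvement, throughout.

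For DLBCL subjects already enrolled, list whether a baseline marrow exists, with its date and type (aspirate, biopsy or both). Flag marrow-confirmed CR and marrow MRD results obtained without one.

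The cost is one sentence changed in two places, carried in a protocol amendment, and one listing. No procedure is added beyond those in the schedules, and no analysis or sample size changes.
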